9.4 CAEPRs

9.4.1 Comprehensive Adverse Events and Potential Risks list (CAEPR) for Pembrolizumab (MK-3475, NSC 776864)

The Comprehensive Adverse Events and Potential Risks list (CAEPR) provides a single list of reported and/or potential adverse events (AE) associated with an agent using a uniform presentation of events by body system. In addition to the comprehensive list, a subset, the Specific Protocol Exceptions to Expedited Reporting (SPEER), appears in a separate column and is identified with bold and italicized text. This subset of AEs (SPEER) is a list of events that are protocol specific exceptions to expedited reporting to NCI (except as noted below). Refer to the 'CTEP, NCI Guidelines: Adverse Event Reporting Requirements' http://ctep.cancer.gov/protocolDevelopment/electronic_applications/docs/aeguidelines.pdf for further clarification. *Frequency is provided based on 3097 patients.* Below is the CAEPR for Pembrolizumab (MK-3475).

NOTE: Report AEs on the SPEER **ONLY IF** they exceed the grade noted in parentheses next to the AE in the SPEER. If this CAEPR is part of a combination protocol using multiple investigational agents and has an AE listed on different SPEERs, use the lower of the grades to determine if expedited reporting is required.

Version 2.7, December 13, 2022¹

Adverse Events with Possible Relationship to Pembrolizumab (MK-3475) (CTCAE 5.0 Term) [n= 3793]		
Likely (>20%)	Less Likely (<=20%)	Rare but Serious (<3%)
BLOOD AND LYMPHATIC SYSTEM DISORDERS		
	Anemia ²	
		Blood and lymphatic system disorders - Other (immune thrombocytopenic purpura) ²
	Lymph node pain ²	
CARDIAC DISORDERS		
		Myocarditis ²
		Pericarditis ²
ENDOCRINE DISORDERS		
	Adrenal insufficiency ²	
		Endocrine disorders - Other (hypoparathyroidism)

Adverse Events with Possible Relationship to Pembrolizumab (MK-3475) (CTCAE 5.0 Term) [n= 3793]		
Likely (>20%)	Less Likely (<=20%)	Rare but Serious (<3%)
	Endocrine disorders - Other (thyroiditis) ² Hyperthyroidism ²	
	Hypophysitis ²	
	Hypopituitarism ²	
	Hypothyroidism ²	
EYE DISORDERS		
		Uveitis ²
		Eye disorders - Other (Vogt-Koyanagi-Harada syndrome)
GASTROINTESTINAL DISORDERS		
	Abdominal pain	
	Colitis ²	
	Diarrhea ²	
	Mucositis oral ²	
	Nausea	
	Pancreatitis ²	
	Small intestinal mucositis ²	
GENERAL DISORDERS AND ADMINISTRATION SITE CONDITIONS		
	Chills ²	
Fatigue		
	Fever ²	
HEPATOBILIARY DISORDERS		
	Hepatobiliary disorders - Other (autoimmune hepatitis) ²	
		Hepatobiliary disorders - Other (sclerosing cholangitis)
IMMUNE SYSTEM DISORDERS		
		Anaphylaxis ²
		Cytokine release syndrome ²
		Immune system disorders - Other (acute graft-versus-host-disease) ^{2,3}
		Immune system disorders - Other (hemophagocytic lymphohistiocytosis) ²
	Immune system disorders - Other (sarcoidosis) ²	
		Serum sickness ²

Adverse Events with Possible Relationship to Pembrolizumab (MK-3475) (CTCAE 5.0 Term) [n= 3793]		
Likely (>20%)	Less Likely (<=20%)	Rare but Serious (<3%)
INJURY, POISONING AND PROCEDURAL COMPLICATIONS		
		Infusion related reaction
INVESTIGATIONS		
	Alanine aminotransferase increased ²	
	Alkaline phosphatase increased	
	Aspartate aminotransferase increased ²	
	Blood bilirubin increased	GGT increased
		Serum amylase increased
METABOLISM AND NUTRITION DISORDERS		
	Anorexia	
	Hyponatremia	
		Metabolism and nutrition disorders - Other (diabetic ketoacidosis) ²
		Metabolism and nutrition disorders - Other (type 1 diabetes mellitus) ²
MUSCULOSKELETAL AND CONNECTIVE TISSUE DISORDERS		
	Arthralgia ²	
	Arthritis ²	
	Back pain	
	Joint range of motion decreased	
	Myalgia ²	
	Myositis ²	
NERVOUS SYSTEM DISORDERS		
		Guillain-Barre syndrome ²
		Nervous system disorders - Other (myasthenic syndrome) ²
		Nervous system disorders - Other (neuromyopathy) ²
		Nervous system disorders - Other (non-infectious encephalitis) ²
		Nervous system disorders - Other (non-infectious meningitis) ²
		Nervous system disorders - Other (non-infectious myelitis)
		Nervous system disorders - Other (optic neuritis)

Adverse Events with Possible Relationship to Pembrolizumab (MK-3475) (CTCAE 5.0 Term) [n= 3793]		
Likely (>20%)	Less Likely (<=20%)	Rare but Serious (<3%)
		Nervous system disorders - Other (polyneuropathy) ² Paresthesia
		Peripheral motor neuropathy ²
RENAL AND URINARY DISORDERS		
		Renal and urinary disorders - Other (autoimmune nephritis) ²
RESPIRATORY, THORACIC AND MEDIASTINAL DISORDERS		
	Cough	
	Pneumonitis ²	
SKIN AND SUBCUTANEOUS TISSUE DISORDERS		
	Bullous dermatitis ²	
		Erythema multiforme ²
	Erythroderma	
		Palmar-plantar erythrodysesthesia syndrome
	Pruritus ²	
	Rash acneiform ²	
	Rash maculo-papular ²	
	Skin and subcutaneous tissue disorders - Other (dermatitis) ²	
	Skin hypopigmentation ²	
		Stevens-Johnson syndrome ²
		Toxic epidermal necrolysis
	Urticaria ²	
VASCULAR DISORDERS		
		Vasculitis ²

Investigators at the time of revision. The current version can be obtained by contacting [contact]. Your name, the name of the investigator, the protocol and the agent should be included in the e-mail.

²Immune-mediated adverse reactions have been reported in patients receiving Pembrolizumab (MK-3475). Adverse events potentially related to Pembrolizumab (MK-3475) may be manifestations of immune-mediated adverse events. In clinical trials, most immune-mediated adverse reactions were reversible and managed with interruptions of Pembrolizumab (MK-3475), administration of corticosteroids and supportive care.

³Acute graft-versus-host disease has been observed in patients treated with Pembrolizumab (MK-3475) who received hematopoietic stem cell transplants.

Adverse events reported on Pembrolizumab (MK-3475) trials, but for which there is insufficient evidence to suggest that there was a reasonable possibility that Pembrolizumab (MK-3475) caused the adverse event:

BLOOD AND LYMPHATIC SYSTEM DISORDERS - Blood and lymphatic system disorders - Other (pancytopenia); Disseminated intravascular coagulation; Hemolysis

CARDIAC DISORDERS - Atrial fibrillation; Cardiac arrest; Chest pain - cardiac; Heart failure; Myocardial infarction; Pericardial effusion; Pericardial tamponade; Ventricular arrhythmia

EYE DISORDERS - Eye pain

GASTROINTESTINAL DISORDERS - Abdominal distension; Ascites; Constipation; Duodenal hemorrhage; Dysphagia; Gastritis; Gastrointestinal disorders - Other (diverticulitis); Gastrointestinal disorders - Other (intestinal obstruction); Gastrointestinal disorders - Other (intussusception); Oral pain; Rectal hemorrhage; Small intestinal perforation; Upper gastrointestinal hemorrhage; Vomiting

GENERAL DISORDERS AND ADMINISTRATION SITE CONDITIONS - Edema face; Edema limbs; Facial pain; Gait disturbance; General disorders and administration site conditions - Other (general physical health deterioration); Generalized edema; Malaise; Non-cardiac chest pain; Pain

INVESTIGATIONS - CPK increased; Cholesterol high; Creatinine increased; Fibrinogen decreased; Lymphocyte count decreased; Neutrophil count decreased; Platelet count decreased; Weight loss; White blood cell decreased

METABOLISM AND NUTRITION DISORDERS - Dehydration; Hypercalcemia; Hyperglycemia; Hyperkalemia; Hypertriglyceridemia; Hyperuricemia; Hypoalbuminemia; Hypokalemia; Hypophosphatemia; Metabolism and nutrition disorders - Other (failure to thrive); Tumor lysis syndrome

MUSCULOSKELETAL AND CONNECTIVE TISSUE DISORDERS - Bone pain; Generalized muscle weakness; Joint effusion²; Musculoskeletal and connective tissue disorder - Other (groin pain); Pain in extremity

NERVOUS SYSTEM DISORDERS - Aphonia; Depressed level of consciousness; Dysarthria; Edema cerebral; Encephalopathy; Headache; Hydrocephalus; Lethargy; Meningismus; Nervous system disorders - Other (brainstem herniation); Seizure; Syncope; Tremor

PSYCHIATRIC DISORDERS - Agitation; Confusion

RENAL AND URINARY DISORDERS - Acute kidney injury; Nephrotic syndrome; Proteinuria; Renal and urinary disorders - Other (hydronephrosis); Urinary incontinence; Urinary tract pain

REPRODUCTIVE SYSTEM AND BREAST DISORDERS - Pelvic pain

RESPIRATORY, THORACIC AND MEDIASTINAL DISORDERS - Dyspnea; Hypoxia; Laryngeal inflammation; Pleural effusion; Pleuritic pain²; Pneumothorax; Respiratory failure

SKIN AND SUBCUTANEOUS TISSUE DISORDERS - Alopecia; Dry skin; Skin and subcutaneous tissue disorders - Other (drug eruption)

VASCULAR DISORDERS - Hypertension; Peripheral ischemia; Thromboembolic event

Note: Pembrolizumab (MK-3475) in combination with other agents could cause an exacerbation of any adverse event currently known to be caused by the other agent, or the combination may result in events never previously associated with either agent.

10.0 DRUG INFORMATION

10.1 Pembrolizumab (MK-3475, NSC 776864)

Availability

Commercial supplies. Pharmacies or clinics shall obtain supplies from normal commercial supply chain or wholesaler.

Pembrolizumab is commercially available. Pembrolizumab (MK-3475) injection is a sterile, preservative-free, clear to slightly opalescent, colorless to slightly yellow solution for intravenous use.

Each vial contains 100 mg of pembrolizumab (MK-3475) in 4 mL of solution. Each 1 mL of solution contains 25 mg of pembrolizumab (MK-3475) and is formulated in: L-histidine (1.55 mg), polysorbate 80 (0.2 mg), sucrose (70 mg), and Water for Injection, USP.

Preparation

Follow institutional standards.

MK-3475 (pembrolizumab) solution for infusion must be diluted prior to administration. Do not shake the vials. Do not use if opaque or extraneous particulate matter other than translucent to white proteinaceous particles is observed. Do not use if discolored. To prepare the infusion solution add the dose volume of MK-3475 (pembrolizumab) to an infusion bag containing 0.9% Sodium Chloride Injection, USP or 5% Dextrose Injection, USP. Mix diluted solution by gentle inversion. The final concentration must be between 1 mg/mL to 10 mg/mL.

Compatible IV bag materials: PVC plasticized with DEHP, non-PVC (polyolefin), EVA, or PE lined polyolefin.

Storage

Store intact vials between 2°C - 8°C (36°F - 46°F). Do not freeze. Protect from light by storing in the original box.

Stability

Store the diluted solution at room temperature for no more than 6 hours from the time of dilution, including room temperature storage of the diluted solution and the duration of infusion, or under refrigeration at 2°C to 8°C (36°F to 46°F) for no more than 96 hours from the time of dilution. Do not shake. Discard after 6 hours at room temperature or after 96 hours under refrigeration.

Administration

IV infusion only. Do not administer as an IV push or bolus injection. If refrigerated, allow the diluted solution to come to room temperature prior to administration.

Infuse over approximately 30 minutes (range: 25 - 40 minutes) using an infusion set containing a low-protein binding 0.2 to 5 micron in-line filter made of polyethersulfone or polysulfone. A central line is not required; however, if a subject has a central venous catheter in place, it is recommended that it be used for the infusion. Do not co-administer other drugs through the same infusion line. Following the infusion, flush the IV line with normal saline.

Adverse Events

See Comprehensive Adverse Events and Potential Risks list (CAEPR) for MK-3475 (pembrolizumab, NSC 776864) CAEPRs in Section 9.4.

Nursing Guidelines

- 1) MK-3475 (pembrolizumab) side effects vary greatly from those of traditional chemotherapy and can vary in severity from mild to life threatening. Instruct patients to report any side effects to the study team immediately. Side effects may be immediate or delayed up to months after discontinuation of therapy. Most side effects are reversible with prompt intervention of corticosteroids.
- 2) Diarrhea can be seen however is less common than that seen with anti-CTLA-4 agents. However it can be severe, leading to colonic perforation. Instruct patients to report ANY increase in the number of stools and/or change in baseline, blood in the stool, abdominal pain to the study team immediately.
- 3) Rash/pruritus/dermatitis is seen. Patients should report any rash to the study team. Treat per section 8.0 and monitor for effectiveness.
- 4) Monitor LFT's closely as elevations in these levels could indicate early onset autoimmune hepatitis. Patients should also be instructed to report any jaundice, or right upper quadrant pain to the study team immediately.

- 5) Pneumonitis can be seen and may be mild (only seen on imaging) to severe. Patients should be instructed to report any SOB, dyspnea, cough, chest pain, etc. to the study team immediately. Patients reporting these symptoms should have a pulse ox checked and consider immediate imaging per the treating MD.
- 6) Endocrinopathies (including hypopituitarism, hypothyroidism, hypophysitis, and adrenal insufficiency) are seen with this agent. Patients may present only with the vague sense of fatigue and “not feeling well.” Additional symptoms may be that of nausea, sweating and decreased activity tolerance. Instruct patients to report these signs or symptoms immediately and obtain appropriate labs as ordered by MD.
- 7) Patients who are started on steroid therapy for any side effects of MK-3475 (pembrolizumab) toxicity should be instructed to take the steroids as ordered, and not to discontinue abruptly as symptoms may return and be severe. Patients may be on steroid therapy for weeks. Instruct patients to report any increase or change in side effects with any dosage decrease as patients may need a slower taper.
- 8) Fatigue is common and may or may not be associated with immune related side effects. Assess patient’s fatigue level prior to each cycle of therapy and report any changes to the study team.
- 9) Patients should avoid receiving live vaccines within 30 days of study drug administration or per other study guidelines.
- 10) Patients who have undergone an allogenic bone marrow transplant, have an increased risk of severe complications including early GVHD, and venoocclusive disease, if they have previously been treated with MK-3475.
- 11) Myocarditis has been reported and associated with MK-3475. Instruct patients to report chest pain, SOB, or dyspnea to study team immediately and/or seek emergency medical attention.

11.0 MEASUREMENT OF EFFECT

Disease should be re-evaluated every 12 weeks after C1D1. Disease response will be made by institutional investigator assessment, based on local radiology review and RECIST v1.1 criteria. Refer to the Study Calendar to determine the allowable scan windows ([Section 5.0](#)). This study uses iRECIST guidelines to guide treatment beyond progressive disease. Irradiated lesion will not be included in RECIST v1.1 or iRECIST evaluation.

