3.2.1 Documentation of disease

- Histologically confirmed metastatic urothelial carcinoma

3.2.2 Patients must be either ineligible for platinum treatment or platinum refractory as defined below:

Platinum-ineligible: If patients meet any one of the following criteria:

1. Impaired renal function [creatinine clearance (CrCl) of <30 mL/min]
2. Grade >2 peripheral neuropathy
3. NYHA Heart Failure of >3

Platinum-refractory: If patients meet any one of the following criteria:

1. Prior platinum-based perioperative chemotherapy within 12 months of relapse
2. Prior platinum-based chemotherapy for metastatic disease

3.2.3 Measurable disease as defined in Section 11.0.

Patients must have at least one measurable site ≥ 1 cm in diameter per RECIST 1.1 and a site targetable for radiotherapy. Measurable site must not overlap with radiated site such that measurable site cannot receive >2 Gy per fraction.

Patients must have measurable disease, defined as at least one lesion that can be accurately measured in at least one dimension (longest diameter to be recorded for non-nodal lesions and short axis for nodal lesions). See Section 11.0 for the evaluation of measurable disease.

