4.6.2 Treatment Assignments

Patients will be randomized 1:1 to the two treatment arms. The factors defined in [Section 4.8.1](#) will be used as stratification factors.

After the patient has been registered into the study, the values of the stratification factors will be recorded, and the patient will be randomized to one of the following treatment groups using the Pocock and Simon dynamic allocation procedure which balances the marginal distributions of the stratification factors between the treatment groups.

- 1) Immunotherapy
- 2) Immunotherapy + Single Site Radiotherapy

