 - 1 The PRO-CTCAE assessment is required for all patients. If the PRO-CTCAE assessment completed prior to registration is obtained \leq 14 days prior to treatment, then the PRO-CTCAE assessment on day 1 of cycle 1 may be skipped. The PRO-CTCAE patient-completed booklet for this protocol can be found on the 'CIRB Approved Documents' tab on the CTSU website.
 - 2 To be completed after registration and \leq 21 days prior to treatment.
 - 3 For women of childbearing potential. Must be done \leq 14 days prior to initiation of study treatment.
 - 4 See Section 6.2.

- 5 Baseline scans can include either: 1) a CT, spiral CT, or MRI and bone scan, or 2) an FDG-PET scan and diagnostic CT performed with both IV and oral contrast, and the CT acquired with 5 mm or less slice thickness. Supporting documentation is to be submitted, per Section 6.1.1.
- 6 ECG prior to registration should be performed if clinically indicated.
 - A All patients receiving immunotherapy will have a urinalysis or urine protein performed \leq 72 hours prior to every dose. If urine protein is \geq 2+, 24-hour urine collection or UPC ratio will be required.
 - B Required only if signs or symptoms suggestive of metastases develop.
 - C \leq 2 days prior to each treatment if accessible to physical examination.
 - D Every 3 months until evidence of progression or relapse. If the baseline scans were a CT or MRI and bone scan, follow-up bone scans are required only for patients with bone metastases as the only site of evaluable disease, and are optional for other patients. Response assessment should include assessment of all sites of disease and use the same imaging method as was used at baseline. Bone imaging (after baseline) is required only if indicative of metastases at baseline or if signs or symptoms suggestive of metastases develop.

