6.4.1 Detailed Steps of Data Submission

Collection of images is required. Alliance A032002 prescribes limited image acquisition requirements, so any imaging acquired is expected to be done per protocol rather than the site's own standard of care. Specifically, PET/CT, CT, MRI and bone scans must be acquired at the following times and subsequently submitted. Supporting documentation must accompany all submissions for this trial. Images will be collected digitally for central archiving and curation. Imaging studies will be collected digitally at the following time points:

1. Baseline – within 42 days before registration
 - a. CT of the chest/abdomen/pelvis
 - i. Intravenous and oral contrast unless contraindicated
 - ii. 5mm of less slice thickness
 - b. Substitutions allowed:
 - i. CT of the chest and MRI of the abdomen/pelvis
 1. Must be diagnostic quality
 2. Intravenous and oral contrast unless contraindicated
 3. 5mm or less slice thickness
 - ii. FDG-PET/CT of the whole body or limited whole body
 1. CT must be of diagnostic quality
 2. Intravenous and oral contrast unless contraindicated
 3. 5mm or less slice thickness
 - c. Bone scan of the whole body
2. Restaging – every 3 months +/- 14 days
 - a. Same imaging as acquired at baseline
 - b. Bone imaging only required if indicative of metastases at baseline or if signs or symptoms develop
3. Progression

4. Confirmatory Follow-up – 12 weeks after evidence of objective response

The complete imaging data set in digital DICOM format will be submitted electronically to the Imaging and Radiation Oncology Core at Ohio (IROC Ohio) within no more than 3 business days upon the image acquisition completeness. BMP files, JPG files, or hard copies (films) are not acceptable. The raw data of the entire study should be saved until the imaging data is accepted by IROC Ohio.

If not using TRIAD, sites need to de-identify the patient data using institutional procedures to remove patient name and medical record number while preserving the Alliance patient ID number (e.g., 112136) and protocol number (e.g., ALLIANCE032002), respectively.

DICOM tag dates and times cannot be altered prior to submission as they are used to put submissions into context regarding patient treatment. Additional changes to DICOM tags prior to submission impede further technical analysis and should be avoided whenever possible.

Imaging data should be submitted electronically to IROC Ohio via TRIAD, Web Transfer or FTP Transfer:

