7.2 Radiotherapy

Administration of radiotherapy will occur to a single site for subjects randomized to the pembrolizumab and radiotherapy group.

Radiotherapy can be initiated after the first dose of immunotherapy and must be completed before 12 weeks after first dose of immunotherapy administered.

There is no size criterion for irradiated site and should follow this priority list:

1. Growing area that may cause symptoms.
2. Area that can tolerate the highest dose prescription (8 Gy x 3) based on normal tissue constraints.
3. If all above equal, then order would be Pelvis, Abdomen, Liver, Lung, Bone.

The goal of RT treatment is to deliver appropriate radiotherapy while minimizing exposure of surrounding normal tissues. Many different ways of delivering RT exist, and all are acceptable as long as the treating institution has completed the necessary credentialing. Most commercially available electron and photon-producing treatment units are allowed. As such, conventional linear accelerators and specialized linear accelerators with image guidance (e.g., Novalis, Trilogy, Synergy, Artiste, TrueBeam, Unity, ViewRay) are allowed. These units can be used with conformal dose delivery or IMRT. Specialized dose painting accelerators (e.g., Cyberknife, or Tomotherapy) are allowed provided they meet the technical specifications of the protocol and are used in a fashion that passes the

credentialing required by the protocol. Conventional linear accelerators without add-on IGRT must have some other IGRT capability like CT-on-rails in the treatment room.

IGRT is required for this study. Either 3DCRT or IMRT (including VMAT) are acceptable planning techniques. IMRT (including VMAT) can result in dosimetric inaccuracies in circumstances where tumor motion is not properly considered. Planning techniques may differ for each lesion to be treated provided that the tumor motion is properly accounted for with each technique when the target or targets are in or near the thorax region.

i. Dose Fractionation

Patients will receive 3 fractions of radiation to a total dose of 24 Gy.

For each metastatic location, Variation Acceptable range is described for plan scoring. Doses falling outside the range of Per Protocol and Variation Acceptable will be scored as Deviation Unacceptable.

There should be a minimum of 40 hours between treatments to any single metastasis.

ii. Technical Factors

Physical Factors

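### The irradiated lesion is dropped from response scoring in Arm B only, and the protocol text does not require the candidate site to be recorded before randomization, so the arms are scored on different lesion sets

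*Combined protocol and SAP*

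**What the plan says.** **Exclusion.** Section 11.0: "Irradiated lesion will not be included in RECIST v1.1 or iRECIST evaluation". Section 7.2: "Administration of radiotherapy will occur to a single site for subjects randomized to the pembrolizumab and radiotherapy group". The exclusion can therefore act only in Arm B.

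**What Arm A scores.** Section 11.1 draws targets from all measurable lesions (at most 2 per organ and 5 in total). Section 11.2 makes everything else non-target. Note D of the study calendar adds "Response assessment should include assessment of all sites of disease and use the same imaging method as was used at baseline". None of these reserves a site in Arm A.

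**Eligibility, both arms.** Section 3.2.3: "Patients must have at least one measurable site ≥ 1 cm in diameter per RECIST 1.1 and a site targetable for radiotherapy", and "Measurable site must not overlap with radiated site such that measurable site cannot receive >2 Gy per fraction", which I read as keeping the two sites apart. Section 3.2.7 bars earlier radiotherapy to either site.

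**Randomization.** Section 4.6.2: "After the patient has been registered into the study, the values of the stratification factors will be recorded, and the patient will be randomized". It mentions no radiotherapy site.

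**Site choice and timing.** Section 7.2 sets no size criterion and ranks first "Growing area that may cause symptoms", then normal-tissue tolerance, then an anatomical order. Radiotherapy may start after the first pembrolizumab dose and must finish before 12 weeks from that dose.

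**Endpoints.** Section 13.2.1 has the treating physician score the primary endpoint by RECIST 1.1, in a trial that Section 13.1 calls open-label. Section 13.7 repeats the analysis with central iRECIST as a key secondary.

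**The concern.** A between-arm comparison of response needs the same scoring rule in both arms. Here one lesion leaves the evaluation in Arm B and its counterpart stays in for Arm A. If that lesion is one that tends to grow, Arm B can show more responses even when radiotherapy does nothing to the other disease. The clinician who settles the site may know the allocation and also reads the primary endpoint. Central review does not cure this, because Section 11.0 applies the same exclusion to iRECIST, and no analysis on a common lesion set is planned. Section 1.1 expects a positive result to lead towards phase 3 and a negative one to end the question, so an artefact of a point or two matters at a one-sided alpha of 0.10.

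**Working it through.** **1. Reproduce the design (Section 13.4).** Inputs: 20% against 40%, one-sided alpha 0.10, power 90%. With pooled variance under the null and z = 1.2816 for both alpha and power:

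n = [1.2816·√(2·0.3·0.7) + 1.2816·√(0.2·0.8 + 0.4·0.6)]² / 0.2² = [1.2816·(0.6481 + 0.6325)]² / 0.04 = 67.3, so 68 per arm and 136 in total. Then 136/0.95 = 143.2, so 144. The plan's figures reproduce.

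**2. Test used.** Single-stratum Mantel-Haenszel statistic with a responders in Arm A, b in Arm B and m = a + b:

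z = (b − m/2) / √V, with V = 68²·m·(136 − m) / (136²·135); reject if z > 1.2816.

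Summing the exact binomial probabilities over all (a, b) gives 0.0999 at 20% against 20% and power 0.906 at 20% against 40%. With the Section 13.6 futility rule (stop if A exceeds B), taken at 34 per arm, these become 0.097 and 0.899.

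**3. What a tilt would do.** Arm A is held at 20%, and Arm B is shifted by the tilt with no effect on non-irradiated disease.

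| Tilt (points) | Type I error | With futility look |
|---|---|---|
| −2 | 0.058 | 0.056 |
| −1 | 0.077 | 0.075 |
| 0 | 0.100 | 0.097 |
| +1 | 0.127 | 0.123 |
| +2 | 0.159 | 0.154 |

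Two points is 0.02 × 68 = 1.36 expected responders in one arm.

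**4. How large the tilt might be.** The documents give no lesion counts, within-patient correlation, share of irradiated sites that would have been targets, or strength of selection. What follows rests on assumptions: 2–5 targets, log size-change SD 0.5, Arm A calibrated to 20%.

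- *Model 1:* half of irradiated lesions are targets, half of dropped targets are replaced, 30% of patients have new-lesion progression, and within-patient correlation is 0.3–0.7. Random site choice gives Arm B 20.2–20.6%. Weak selection on growth (correlation 0.1–0.3 with later growth) gives 20.3–21.6%.
- *Model 1 with every dropped target replaced and random choice:* type I error 0.099–0.101, so no tilt.
- *Model 2:* no replacement, no new-lesion progression, within-patient correlation 0.5–0.9, half or all irradiated lesions targets. Random choice gives +0.2 to +2.1 points. Selection on growth (correlation 0.5) in half or all patients gives +0.6 to +7.2. Selection of better-responding sites gives −0.1 to −2.5.

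**5. How far selection can follow on-study growth.** Count from the first dose. Radiotherapy must finish before day 84. Section 11.0 re-evaluates every 12 weeks (day 84), and Section 6.4.1 says "Restaging – every 3 months +/- 14 days", so the earliest scan is about day 77 (3 months less 14 days) or day 70 (12 weeks less 14 days). Three fractions at least 40 hours apart span at least 2 × 40 = 80 h = 3.3 days. That leaves 7 − 3.3 = 3.7 or 14 − 3.3 = 10.7 days to read the scan, plan and start. Selection on growth would mostly rest on growth before baseline or growth that is clinically evident.

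**The case against.** The strongest reply is that the size is assumed and the sign is open. That stands. The modelled ranges move widely with inputs that the documents do not supply, and choosing a better-responding lesion would work against Arm B.

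Several features also shrink any tilt, and these stand too. Only the first item in the Section 7.2 list concerns growth. With no size criterion, the irradiated site may be small or non-measurable; if it is non-target it bears only on complete response and non-target progression. Section 3.2.8 has symptomatic lesions amenable to palliative radiotherapy treated before enrollment. Targets may be chosen from other disease where it exists. Arm B patients who are never irradiated lose no lesion.

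A reader might infer that no site is considered before allocation. The documents do not support that: Sections 3.2.3 and 3.2.7 presuppose a site in every patient, and Section 4.4 has eligibility verified before registration. What the protocol text lacks is a requirement to record the site. A form might capture it, but the forms are outside the documents.

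A reader might also infer that the primary endpoint should be redefined with the exclusion in both arms. That goes too far. It would ignore real growth of an untreated Arm A lesion and change what the 20% control rate refers to. It could also collide with the progression rules: Section 8.1.6 removes patients who require radiotherapy during treatment as progression, and Section 12.2 stops treatment on iRECIST progression.

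None of this removes the asymmetry itself, which is plain in the text.

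**Conclusion.** The concern holds as a gap in comparability. One lesion is left out of response scoring in Arm B only, that lesion can be chosen after open-label allocation, and the protocol text requires no pre-randomization record from which a matched comparison could be made. It touches the primary endpoint and the key secondary endpoint.

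The asymmetry is certain; its effect is not. It probably favours Arm B because a growing area ranks first, but it may be nil (dropped targets replaced, choice unrelated to growth) or reversed. The type I errors of 0.058 to 0.159 for −2 to +2 points show sensitivity; they do not estimate what will happen. The documents therefore do not support saying that the false-positive rate is inflated by a known amount, or that a positive result would be an artefact. Excluding the irradiated lesion is itself right.

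It is worth fixing because the remedy is small and cannot be credibly rebuilt later: naming an Arm A site once outcomes are known would not convince.

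**What to change.** 1. Before randomization, record in both arms the candidate radiotherapy site that Sections 3.2.3 and 3.2.7 already presuppose.
2. Keep the primary definition. Prespecify in Sections 13.6 and 13.7 a sensitivity analysis of RECIST 1.1 response and central iRECIST response that leaves the designated lesion out of the baseline sum and of follow-up scoring in both arms.
3. In Arm B, also leave out the lesion actually irradiated if it differs from the designated one. Report how often this happens, and note that some asymmetry remains in those patients.
4. State in Section 11.1 that the baseline sum is formed without the irradiated lesion. State also that the matched exclusion serves the sensitivity analysis only and does not affect progression calls or treatment decisions under Sections 8.1.6, 11.7 or 12.2.

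**Cost.** One form field, a short site judgement for Arm A patients, one extra analysis and a few sentences. No extra scans are needed, because Section 6.4 already requires image submission for all registered patients. The sample size, the 20% control rate, the site-selection list and treatment are unchanged.
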